10.3 Exploratory Analyses

All efficacy analyses at time points other than Week 14 are considered exploratory as described above.

Additional exploratory efficacy endpoints include:

- FIQR total score, overall impact domain score, and individual item scores at all post-randomization clinic visits
- Proportion of patients with a $\ge 30\%$ improvement from baseline to Weeks 1-14 in the daily self-reported pain severity score
- Proportion of patients with a ≥50% improvement from baseline to Weeks 1-14 in the daily self-reported average pain severity scores
- Proportion of patients with a PGIC rating of "minimally improved," "very much improved" or "much improved" at all post-randomization clinic visits
- PGIC as a continuous variable with 1-7 scoring
- CSFQ-14 at Week 14
- In-clinic assessment of pain (24-hour & weekly recall)

The PGIC, 30% and 50% improvement responder endpoints will be analyzed with a difference in proportions Z test (equivalent to a Pearson's Chi Squared). Patients with missing data will be considered non-responders. The percentages of responders and the 95% CIs of the percentages as well as the difference in the percentages and its 95% CI will be reported.

In addition to the responder analysis in the secondary outcomes, PGIC will be analyzed as a continuous variable scoring the responses 1-7. Results will be reported by treatment with summary statistics and an MMRM Model will be used to compare treatments. The model will include the fixed, categorical effects of treatment, pooled site, study week, and treatment by study week interaction. An unstructured covariance structure will be used to model the within-patient errors. If this analysis fails to converge, the following structures will be tested in this order: first order ante dependence, heterogeneous first order autoregressive, heterogeneous compound symmetry and compound symmetry with the first to give convergence used. The Kenward-Roger approximation will be used to estimate the denominator degrees of freedom. Significance testing will be based on least-squares means using a two-sided alpha=0.05 test and two-sided 95% confidence intervals will be presented.

The CSFQ-14 is completed at baseline and Week 14/ET. It has a male and a female version, which will be analyzed separately. The CSFQ-14 will be analyzed for its total score, three subscales on phases of sexual response, and five subscales for dimensions of sexual functioning by using an Analysis of Covariance (ANCOVA) model. The model will include the fixed, categorical effects of treatment and pooled site, plus a baseline covariate corresponding to the subscale (or total) being analyzed. Significance testing will be based on least-squares means using a two-sided alpha=0.05 test and two-sided 95% confidence intervals will be presented. This outcome is considered to be supportive of the product's safety; other exploratory analyses are for further support of product efficacy.

[figure not shown]
Protocol: TNX-CY-F307 Page 29 of 45

Final v1.0

The FIQR exploratory endpoints and the in-clinic pain assessments will be analyzed using an MMRM including the fixed, categorical effects of treatment, pooled site, study week, and treatment by study week interaction, as well as the fixed covariates of baseline value and baseline value score-by-study week interaction. An unstructured covariance structure will be used to model the within-patient errors. If this analysis fails to converge, the following structures will be tested in this order: first order ante dependence, heterogeneous first order autoregressive, heterogeneous compound symmetry and compound symmetry with the first to give convergence used. The Kenward-Roger approximation will be used to estimate the denominator degrees of freedom. Note that the screening values will be used as baseline for the in-clinic pain outcomes.

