12.2.2. Patient Global Impression of Change (PGIC)

The PGIC is a FM-specific validated instrument to gauge the patient's assessment of change in condition. This form will be completed by the patient at Visits 3, 4, 5 and 6. The patient will answer a single question:

Since the start of the study, overall my fibromyalgia is:

- 1 = Very much improved
- 2 = Much improved
- 3 = Minimally improved
- 4 =No change
- 5 = Minimally worse
- 6 = Much worse
- 7 =Very much worse

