8.1.1 Adjustments for Multiplicity

8.1.1.1 Multiplicity

To adjust for multiplicity and to control for overall type I error, a sequential test procedure will be applied to the primary and key secondary efficacy endpoints. If the primary analysis produces a result that is statistically significant at the two-sided 0.05 level, a significance level of 0.05 will be used for comparing the secondary endpoints in an ordered fashion. If the analysis for a secondary endpoint does not produce a statistically significant result (p-value < 0.05), then the remaining secondary endpoint analyses will automatically be considered non-significant regardless of the p-value produced.

The order of key secondary endpoints in which they are to be tested is as follows:

- Proportion of patients with a PGIC rating of "very much improved" or "much improved" at Week 14
- Change from baseline in the FIQR symptoms domain score at Week 14
- Change from baseline in the FIQR function domain score at Week 14

Protocol: TNX-CY-F307 Page 18 of 45

Final v1.0

- Change from baseline in the PROMIS score for sleep disturbance at Week 14
- Change from baseline in the PROMIS score for fatigue at Week 14
- Change from baseline to Week 14 in the weekly average of the daily diary assessment of sleep quality.

No other adjustments for multiplicity will be made and other p-values displayed in the output will be considered for descriptive summary purposes only and will not be used for formal inference. Additional details regarding statistical analysis for the listed endpoints can be found in Section 10.

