8.2.3 Patient Global Impression of Change (PGIC)

PGIC is a question completed by the patient at Weeks 2, 6, 10, and 14. The patient will rate the change in their overall fibromyalgia symptoms on a 1-7 Likert scale, where 1 is "Very Much Improved" and 2 is "Much Improved". Scores of 1 and 2 will be considered PGIC responders, and all other scores will be considered non-responders for that visit. The proportion of responders in each treatment arm will be analyzed. Any missing PGIC score will be considered a non-responder for that visit.

Protocol: TNX-CY-F307 Page 22 of 45

Final v1.0

An exploratory analysis will include "Minimally Improved" (3) as responders, in addition to scores of 1 and 2.

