13. CHANGES FROM PLANNED ANALYSIS

Analysis of PGIC as a continuous variable with values 1-7 added.

Protocol: TNX-CY-F307 Page 38 of 45

Final v1.0

14.	REFERENCES	(AVAILABLE	UPON REC	DUEST)
-----	------------	------------	-----------------	--------

1
-
_
_

Protocol: TNX-CY-F307 Page 39 of 45

Final v1.0

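### The exploratory MMRM of PGIC scored 1-7 has no baseline severity covariate; adding baseline diary pain would cost almost nothing, for a gain of unknown size

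*SAP*

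**What the plan says.** SAP 10.3 states that "PGIC will be analyzed as a continuous variable scoring the responses 1-7". For the repeated-measures model it says: "The model will include the fixed, categorical effects of treatment, pooled site, study week, and treatment by study week interaction". No baseline covariate follows. Later in the same section, the exploratory FIQR and in-clinic pain models list the same effects and then continue "as well as the fixed covariates of baseline value and baseline value score-by-study week interaction". The primary model (SAP 10.1.2) and the continuous key secondary models (SAP 10.2, by reference to the primary) also carry baseline and baseline-by-week terms. The CSFQ-14 ANCOVA in SAP 10.3 includes the baseline of the score being analysed.

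The reason for the difference is visible. SAP 8.2.3 says "PGIC is a question completed by the patient at Weeks 2, 6, 10, and 14", so there is no pre-treatment value. The item in Protocol 12.2.2 reads "Since the start of the study, overall my fibromyalgia is", so the score is itself a rating of change.

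On status, SAP 10.3 says of this model "Significance testing will be based on least-squares means using a two-sided alpha=0.05 test". SAP 8.1.1.1 says that, outside the ordered sequence, "other p-values displayed in the output will be considered for descriptive summary purposes only". SAP 13 records the analysis as an addition: "Analysis of PGIC as a continuous variable with values 1-7 added".

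**The concern.** A covariate does not have to be the same instrument as the outcome. It has to be measured before randomization, and it helps to the extent that it predicts the outcome. Baseline diary pain meets the first condition. It is already derived for the primary analysis (SAP 8.2.1), and a patient needs scores on at least 5 of the 7 preceding days to be randomized (SAP 4.2).

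Randomization is stratified by center only (Protocol 7.3), so the design does not balance baseline pain beyond what chance provides. The other MMRMs would adjust for an imbalance in their own baseline; the PGIC model has no severity term with which to do so. At stake are the width of the interval, and the conditional accuracy of the estimate, in one supportive analysis.

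**Working it through.** **Nothing to reproduce.** The visible text gives no SD, effect size, power or precision for PGIC. The sample size appears only as 235 per arm, and 2 × 235 = 470.

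**Inputs.** From the documents: n = 235 per arm, two-sided alpha 0.05. Assumed: ρ, the correlation of baseline diary pain with Week 14 PGIC within arm and site. The documents do not give it, so a range that includes zero is shown.

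**Step 1: precision.** With one baseline covariate the residual variance is multiplied by 1 − ρ², and the standard error by √(1 − ρ²). The outcome SD cancels. For a treatment difference that has 80% power without the covariate, power becomes Φ((1.960 + 0.842)/√(1 − ρ²) − 1.960). The simulation used one visit, 470 patients and 30 sites, adjusting for site with and without the covariate.

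| Assumed ρ | Variance reduction | SE reduction | Power (80% unadjusted) | Simulated SE ratio |
|---|---|---|---|---|
| 0 | 0% | 0% | 80.0% | 1.001 |
| 0.1 | 1% | 0.5% | 80.4% | 0.996 |
| 0.2 | 4% | 2.0% | 81.6% | 0.981 |
| 0.3 | 9% | 4.6% | 83.6% | 0.955 |
| 0.5 | 25% | 13.4% | 89.9% | 0.866 |

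Example for ρ = 0.3: √(1 − 0.09) = 0.954, so the SE falls by 4.6%. Power is Φ(2.802/0.954 − 1.960) = Φ(0.977) = 83.6%.

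**Step 2: cost when the covariate is useless.** One estimated slope inflates the variance by about 1 + 1/466. Break-even is (1 − ρ²)(1 + 1/466) = 1, which gives ρ² = 1/467 and ρ ≈ 0.05. At ρ = 0 the simulated loss is 0.1% of the SE.

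**Step 3: chance imbalance.** In baseline SD units, the between-arm difference in mean baseline pain has standard error √(2/235) = 0.092, ignoring the site adjustment. An imbalance of 1.96 × 0.092 = 0.181 SD or more, in either direction, occurs in 5% of randomizations. Without the covariate it moves the PGIC difference by ρ × 0.181 outcome SDs:
- ρ = 0.1: 0.018 SD, or 0.1 × 1.96 = 0.2 standard errors.
- ρ = 0.3: 0.054 SD, or 0.3 × 1.96 = 0.6 standard errors.

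Averaged over randomizations this shift is zero. The unadjusted comparison is therefore unbiased; the covariate removes the shift in the particular sample obtained.

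**The case against.** The strongest objection is that nothing here is wrong. The SAP follows one rule throughout: adjust for the outcome's own baseline where one exists. PGIC has none, and no other model borrows the baseline of a different instrument. That stands. A reader might infer from the contrast with the other MMRMs that the plan is inconsistent, and the documents do not support that reading.

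A reader might also infer that the plan is throwing away precision. The documents do not support that either, because the loss depends wholly on a correlation they do not report. They also give two reasons to expect a weak one. PGIC already rates change, so the starting level of pain may say little about it. And baseline pain is restricted at entry to a mean of 4 to 9, with at most two days below 4 and no score of 10 (SAP 4.2), which tends to weaken correlation. A gain near zero is plausible.

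Restating the gain as extra patients would overstate it. For ρ = 0.3, 470/(1 − 0.09) = 516.5, or about 46 more. But this analysis has no visible power target, and not every patient will have a Week 14 PGIC.

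Finally, the choice of diary pain over, say, baseline FIQR is a judgement. Diary pain is suggested because it is a condition of randomization, is already derived, and is the primary measure.

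What survives is the asymmetry: the covariate costs almost nothing if it turns out useless, and helps if it does not.

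**Conclusion.** This is a minor, optional improvement. The model has no baseline severity term, a suitable pre-randomization covariate exists for essentially every patient, and including it would not bias the randomized comparison. The SE reduction is about 0% to 5% for assumed correlations of 0 to 0.3. A correlation of 0.5, for which the documents offer no evidence, would be needed to reach 13%. These figures rest on the assumed correlation and on a linear single-visit approximation to the repeated-measures model.

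A reader might take the point to touch PGIC as the first key secondary endpoint. It does not. That endpoint is the Week 14 responder proportion, compared by a difference-in-proportions test (SAP 10.2), and nothing here alters it. Leaving the covariate out of the exploratory model affects neither type I error nor any formal conclusion.

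**What to change.** In SAP 10.3, extend the effects of the continuous PGIC model with baseline weekly-average diary pain, as defined in SAP 8.2.1, and its interaction with study week. Note this in SAP 13 beside the existing entry for the analysis. Make the change before unblinding. If treatment codes have already been opened, keep the stated model as the reported one and present the adjusted model as a post-hoc analysis, labelled as SAP 2 and 5 require.

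The cost is one phrase and, with four PGIC visits, four more fixed-effect parameters (one main effect and three interaction terms). No new data collection or derivation is needed.

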5. INTRODUCTION

5.1. Overview of Fibromyalgia

Fibromyalgia (FM) is a musculoskeletal pain disorder of unknown etiology. The prevalence of FM in the United States (US) is estimated at 2%; occurring in approximately 3.4% of females and 0.5% of males (Wolfe, et al. 1995). In addition to diffuse myalgia, FM is characterized by chronic fatigue, psychological distress, and disturbed and unrefreshing sleep (Wolfe, et al. 2010; Wolfe, et al. 1995; Campbell, et al. 1982; Smythe, et al. 1985). Potential triggers of FM include psychological factors (Payne, et al. 1982; Ahles, et al. 1984; Wolfe, et al. 1984), mechanical stresses in the cervical and lumbar spine (Lewis, et al. 1939), muscle deconditioning (Bennett, et al. 1989), neurotransmitter abnormalities (Russell 1989), and disturbances in the chronobiology of sleep-wakefulness (Moldofsky 1994).

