7.3. Number of Patients and Treatment Assignment

Approximately 470 patients will be randomized in a 1:1 ratio to treatment with TNX-102 SL 5.6 mg (2 x 2.8 mg tablets) or SL placebo tablets. Randomization will be stratified by center. Randomized patients who withdraw will not be replaced. Each patient will participate for 17-21 weeks in an outpatient clinic setting. This includes a variable 1 to 5-week screening and washout period, a 14-week treatment period, and a 2-week safety follow up period.

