4. OVERALL STUDY DESIGN AND PLAN

This is a Phase 3, randomized, parallel-group, double-blind, placebo-controlled, 16-week study designed to evaluate the efficacy and safety of TNX-102 SL 5.6 mg (2 x 2.8 mg tablets) taken daily at bedtime for the treatment of fibromyalgia. The study is to be conducted at approximately 30-40 investigational sites in the United States.

The study will consist of a Screening Visit (Visit 1, Days -35 to -8), a Baseline/Randomization Visit (Visit 2, Day 1), a Week 2 Visit (where the dose will be increased to 5.6 mg/day), and 3 more treatment visits (Weeks 6, 10 and 14 or Early Termination). The period between the Screening and Baseline Visit wills be at least 7 days, in order to allow for at least one week of daily pain data collection, and up to 35 days, to accommodate any necessary scheduling challenges or prohibited medication washout time. For extenuating circumstances, the duration of the Screening period may be increased to up to 49 days with Medical Monitor approval, and an option for a telephone visit will be available for Weeks 2, 6, and 10 for those unable to attend an in-clinic visit due to circumstances related to the COVID-19 pandemic. Additionally, a Week 14/ET telephone visit or home visit by site staff may be allowed on a case-by-case basis, approved by the Medical Monitor, if the only other choice is losing the patient completely from the study if patient absolutely cannot come in to the clinic for the visit. A safety follow up telephone visit will occur at Week 16. The total duration of the study, including Screening, will be approximately 17-21 weeks. The maximum treatment duration will be 14 weeks.

Eligible patients who provide written consent will have study assessments performed at Screening and will stop all excluded medications during the washout period, as required, through the Week 14 visit (Visit 6). An in-clinic 7-day recall NRS average daily pain intensity score at Screening must be ≥ 4 and ≤ 9 in order for the patient to remain eligible.

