8.1.3 Site Covariate

For the purposes of modeling and imputation, all sites with less than 10 patients will be pooled into a single large site. In listings and analyses by site, patients will appear under their study site identifier (not the pooled site).

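### The male CSFQ-14 ANCOVA keeps a fixed effect for each site pooled on patients of both sexes, leaving probably only 2-3 males per site level and noticeably wider intervals for males

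*SAP*

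**What the plan says.** SAP 10.3 describes the CSFQ-14 analysis. On the two versions of the questionnaire it says: "It has a male and a female version, which will be analyzed separately". The total score, three phase subscales and five dimension subscales each get an ANCOVA. On its terms: "The model will include the fixed, categorical effects of treatment and pooled site, plus a baseline covariate". On testing: "Significance testing will be based on least-squares means using a two-sided alpha=0.05 test", with 95% intervals. There is one post-baseline value, at Week 14 or early termination.

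The site factor comes from SAP 8.1.3: "all sites with less than 10 patients will be pooled into a single large site". The count is of all patients at the site. Neither section gives a separate pooling rule, or a fallback model, for an analysis restricted to one sex. The repeated-measures models in the same section do have an ordered list of fallback covariance structures.

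On design, Protocol 7.3 states "Approximately 470 patients will be randomized in a 1:1 ratio" and "Randomization will be stratified by center". SAP section 4 adds: "The study is to be conducted at approximately 30-40 investigational sites in the United States". The only figure by sex is the population prevalence in Protocol 5.1: "occurring in approximately 3.4% of females and 0.5% of males".

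**The concern.** A threshold of 10 patients is sensible for a model fitted to everyone. It does not protect a model fitted to a small subset, because a site with 15 patients keeps its own term in the male model even if it enrolled one male. With fixed site effects, treatment is compared only within site levels. A male who is alone in his level, or whose fellow males there are all in the same arm, tells the model about his site and nothing about treatment. Randomization is stratified by center and not by sex, so nothing balances the arms among the males of one site.

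At stake is the precision of the male sexual-function comparison. The SAP describes this outcome as supporting safety and lists it among the safety data in section 11. In a safety comparison, lost precision is not conservative: a needlessly wide interval can be read as the absence of a signal.

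**Working it through.** The documents give no power, precision or expected number of males for this analysis, so there is no planned figure to reproduce.

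**Inputs from the documents.** 470 patients, 1:1; 30-40 sites (470/40 = 11.8 to 470/30 = 15.7 patients per site); pooling below 10 patients in total; model terms treatment, pooled site and baseline; prevalence 3.4% in females and 0.5% in males.

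**Assumptions.**
- Male share: 0.5/(3.4 + 0.5) = 12.8%, taking equal numbers of men and women in the source population. This gives 0.128 × 470 ≈ 60 males. Because it is only an inference, 5%, 10% and 20% are shown as well.
- Males with a Week 14/ET value: 80% or 100% (0.8 × 60 = 48, or 60).
- Blocks of 4 within center; even or uneven recruitment across sites.
- Equal residual variance with and without site, that is, site explains no outcome variance.

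**Formulas.** Let a and b be the numbers of active and placebo males in a site level, M the males with data, and L the site levels that contain at least one of them.
- Treatment information with site: sum over levels of ab/(a + b). Without site: AB/(A + B), where A and B are the arm totals among males.
- Residual degrees of freedom: M − L − 2 with site, M − 3 without.
- Interval-width ratio: [t(0.975, df with site)/t(0.975, df without)]/√(retained information).

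**Simulation of the actual pooling rule** (500 runs per case; ranges run over 30, 35 and 40 sites, even and uneven recruitment, and 80% or 100% with data):

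| Male share | Information retained | Interval width, with site relative to without |
|---|---|---|
| 5% | 29-46% | 1.6-2.7 |
| 10% | 46-64% | 1.27-1.57 |
| 12.8% | 53-70% | 1.20-1.42 |
| 20% | 67-81% | 1.11-1.24 |

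At 12.8%, pooling leaves about 22-31 site levels, of which about 19-27 contain males, so there are 2-3 males per level. About 23-44% of males sit in a single-arm level. Residual degrees of freedom are about 22-38 with site and 45-58 without. At 5% only about 3-8 remain with site.

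**Check by hand.** If arms were allocated by simple randomization, a level with n males would carry expected information (n − 1)/4. The retained fraction is then about (M − L)/(M − 1).
- 35 sites, even recruitment, 80% with data: M = 48.1 and L = 24.4 give 23.7/47.1 = 0.50 (simulated 0.527).
- 35 sites, uneven recruitment, all with data: M = 60.2 and L = 20.3 give 39.9/59.2 = 0.67 (simulated 0.699).

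The simulated values are slightly higher, as expected when blocking within center gives some balance. For the first case the width ratio is (2.076/2.014)/√0.527 = 1.42, as simulated.

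**Females, for comparison.** About 328 with data: 97-98% of the information is retained and the interval is 1.01 times as wide. The problem is specific to males.

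**The case against.** The strongest reply is that the planned model is conventional. Center is the stated stratification factor, and pooled site appears in all the model-based comparisons the SAP describes. Dropping it for one sex gives males and females different models, and any real site effect would narrow the gap shown above. The outcome is exploratory, SAP 8.1.1.1 makes p-values outside the hierarchy descriptive only, and adverse events are tabulated separately. All of that stands, and it limits the consequence. The variance argument does not remove the point, however: ignoring the small t-quantile difference, site would have to explain about 30-47% of the males' residual variance to break even (100% minus the 53-70% retained). Nothing in the documents suggests that.

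A reader might also infer stronger things that the documents do not support.
- That 13% is a ceiling on the male share. It is a population-prevalence ratio; no enrolment target by sex is stated and recruitment need not follow prevalence.
- That sites without males also use up degrees of freedom. A site level with no males with data has no observations in the male model and costs nothing.
- That the male treatment effect may well be non-estimable. In simulation this occurred in roughly 7-19% of runs at 5% male, in under 0.1% at 10%, and in none at 12.8% or 20%.
- That the estimate is biased. It is not; the loss is one of precision.

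**Conclusion.** The point holds as a matter of efficiency in one exploratory analysis that supports safety. The site term in the male CSFQ-14 model costs about 30-47% of the treatment information and widens 95% intervals by about 20-42% if enrolment follows the protocol's prevalence figures. The size depends on the unplanned male share: modest at 20%, severe at 5%, and only near 5% is estimability itself a real risk. It also rests on the assumed 80-100% with data, the assumed block size, and site explaining no outcome variance. The primary and key secondary results and the female CSFQ-14 model are not affected to any relevant degree. Priority is low, but the remedy is cheap.

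**What to change.** In SAP 10.3, state that the male CSFQ-14 ANCOVA includes treatment and baseline only, and that the female model keeps pooled site. At a 12.8% male share this would narrow the male interval by about 17-30% (1 − 1/1.20 to 1 − 1/1.42) under the same assumptions. An alternative that keeps some site adjustment is to re-pool sites for this model on the number of males with data; a random site effect is a further option.

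The cost is one phrase in the SAP. Counts of males by site can be reviewed without treatment codes, so the sponsor can settle the choice before unblinding. The downside is small: no adjustment, or a coarser one, for the stratification factor in males.
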